11.6 Handling of Drop-Outs

Drop-outs are accounted for in the sample size calculation. Therefore no additional replacement of drop-out is planned.

12 DATA QUALITY ASSURANCE AND CONTROL

The Sponsor-Investigator is implementing and maintaining quality assurance and quality control systems with written SOPs and Working Instructions to ensure that trials are conducted and data are generated, documented (record), and reported in compliance with the investigation plan, ISO EN 14155, and applicable regulatory requirement(s).

Monitoring and Audits will be conducted during the course of the study for quality assurance purposes.

12.1 Data Handling and Record Keeping / Archiving

The study will strictly follow the investigation plan. If any changes become necessary, they must be laid down in an amendment to the investigation plan. All amendments of the investigation plan must be signed by the Sponsor-Investigator and submitted to CEC.

12.1.1 Case Report Forms

In the current study, eCRFs based on the data capture software REDCap [92] will be used. The software meets the requirements of good clinical practice. It is the responsibility of the PI to ensure correctness and completeness of the recorded data. After data recording, all data must be entered into eCRF as soon as possible. The name of the patient will not be visible in the eCRF. Personal data is encoded using a subject identifier. Study-related patient documentation and the signed informed consent form is to be stored in a patient specific folder. All data in the eCRF must be noted in the patient's medical file. All essential documents of the trial must be stored for a minimal duration of 15 years starting from study close-out. Patient's medical files must be stored for the maximum duration applicable at the clinic. The subject identifier key is stored in form of an enrolment-log on a different server than the eCRFs. Access is password restricted.

12.1.2 Specification of Source Documents

The following documents are considered source data, including but not limited to:

- SAE worksheets

- Nurse records, records of clinical coordinators, and
- Medical records from other department(s), or other hospital(s), or discharge letters and correspondence with other departments/hospitals, if participant visited any during the study period and the post study period.

Source data must be available at the site to document the existence of the study participants and substantiate the integrity of study data collected. Source data must include the original documents relating to the study, as well as the medical treatment and medical history of the participant.

The following information (at least but not limited to) should be included in the source documents:

- Demographic data (age, sex)
- Inclusion and Exclusion Criteria details
- Participation in study and signed and dated Informed Consent Forms
- Visit dates
- Medical history and physical examination details
- Key efficacy and safety data (as specified in the investigation plan)
- AEs and concomitant medication
- Results of relevant examinations
- Laboratory printouts
- Dispensing and return of study device details
- Reason for premature discontinuation
- Randomization number

12.1.3 Record Keeping / Archiving

All essential documents of the clinical trial will be stored for a duration of at least 15 years. Patient medical files and other source data will be stored for the maximal time allowed by the University Hospital Balgrist. Printed patient medical files will be archived in an access restricted area. The patient medical file software (KISIM) and the study data capture software (REDCap) are access restricted.

12.2 Data Management

12.2.1 Data Management System, access and back-up

Subject-related data will be stored in the research electronic data capture software REDCap [92]. The PI is responsible for data recording. The PI will grant the relevant personnel user rights to view, edit or overwrite data entries by password as applicable. All edits will be automatically documented in the change history log.

12.2.2 Analysis and Archiving

For data analysis, subject-related data from REDCap will be exported and analyzed in statistics software (IBM - SPSS). Before data export, all patient identifiers will be removed. CT- and radiographic images will be analyzed using image analysis software (3D Slicer [83], MATLAB). All eCRF data will be stored for a minimum of 15 years in a safe storage facility at an external location. In-house archiving of research related data and responsibilities are outlined in the clinic's WI: UCAR_WI_013_Archiving_01.

12.3 Monitoring

Regular monitoring visits at the investigator's site prior to the start and during the course of the study will help to follow up the progress of the clinical study, to assure utmost accuracy of the data and to detect possible errors at an early time point. The Sponsor-Investigator organizes professional independent monitoring for the study.

All original data including all patient files, progress notes and copies of laboratory and medical test results must be available for monitoring. The monitor will review all or a part of the eCRFs and written informed consents. The accuracy of the data will be verified by reviewing the above referenced documents.

A quality assurance audit/inspection of this study may be conducted by the competent authority or CEC, respectively. The quality assurance auditor/inspector will have access to all medical records, the investigator's study related files and correspondence, and the informed consent documentation that is relevant to this clinical study.

The investigator will allow the persons being responsible for the audit or the inspection to have access to the source data/documents and to answer any questions arising. All involved parties will keep the patient data strictly confidential.

12.4 Confidentiality, Data Protection

Direct access to source data may be granted in the case of monitoring, audit or inspections. All personnel must treat patient data as confidential. As far as possible, encoded data will be used. Only persons listed on the staff list have access to the source data.

12.5 Storage of Related Health Data

All health-related patient data will be stored and archived in the data capture software REDCap. Patient-source data will be registered using subject identifiers. After full data analysis, all subject identifiers will be erased. Patient-source data may still be saved in the patient's medical record. Collection, disclosure, storage of patient-related data are carried out in accordance with Swiss data protection regulations and the Human Research Act. A requirement is the informed consent of every subject prior to inclusion in the clinical trial.

13 PUBLICATION AND DISSEMINATION POLICY

The sponsor-Investigator will make every effort to publish the data of the interim analysis, the primary endpoint analysis and the full data analysis in a peer-reviewed medical journal. No statistical codes or record IDs of study participants will be published. No trade secrets will be disclosed.

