6.3.2 Blinding Procedures

The current clinical trial is designed as a patient-blinded study.

Group allocation cannot be blinded to the operator nor can the group allocation be blinded to the practitioner evaluating the radiological images at regular postsurgical follow-up visit and for safety assessment.

Concealment of group allocation to the patient is ensured. During surgery, graft preparation and graft insertion is outside the patient's field of view.

No radiological images will be shown to the patient as to not reveal group allocation.

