9.2.2.2 Assessment of Knee Stability

KT-1000 Arthrometer-, Lachman- and Pivot-shift testing are performed by the PI. All tests are performed first on the involved and secondly on the normal contralateral side.

KT-1000 Arthrometer testing is performed with the patient in supine position on a firm examination table. The knee is flexed to an angle between 20° and 35°. The thighs rest on a support platform. The KT-1000 Arthrometer testing device is then strapped to the anterior aspect of the tibia. After zeroing of the machine, tibial anterior displacement is measured. The measurement is performed once, and the results are noted in millimeters on the respective eCRF.

Lachman testing is performed by manual anterior displacement of the tibia in 15° flexion. The calf is grasped with one hand and quickly pulled anteriorly, while the other hand constrains the movement of the thigh. The test is performed once. The results are noted in the respective eCRF using the grading system displayed below.

Grade	Displacement
0	<3 mm
1	3 - 5 mm
2	>5 mm

For Pivot-shift testing, the anteriorly subluxated tibia head is repositioned manually. While a manual force is applied for internal rotation, valgisation and axial pressure, the knee is flexed manually from full extension. The rolling-gliding motion is assessed. The test is performed once. The results are noted in the respective eCRF using the grading system displayed below.

Grade	Finding
0	Normal
1	Glide
2	Clunk
3	Gross clunk with locking

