11.2 Determination of Sample Size

For the power calculation a dedicated software (G*Power [84]) was used. It is aimed to detect a 20% difference in relative change of bone tunnel volume between the two groups. Pooling the standard deviations of the percentage volume change of different bone tunnel sections (articular/outside third) and two different tunnels (anteromedial/posterolateral tunnel) from the study conducted by Araki et al. [85] yields an estimate for the overall standard deviation of $\pm 25.175\%$. With a type I error rate of $\alpha=0.05$ and a power of $1-\beta = 0.8$ and assuming both samples to be normally distributed and having equal variances, the required sample size per group is $n = 25$.

Accounting for a drop-out rate of 10% the total number of subjects for equally sized groups to be acquired is $N = 56$.

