11.3 Statistical Criteria of Termination of Trial

Statistically significant inferiority ($P \leq 0.05$) of the interventional treatment determined at 4.5 months follow-up on the primary efficacy outcome with a total of 20 patients (10 interventional, 10 control) will lead to premature termination of the study.

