11.4 Planned Analyses

In all statistical analyses testing a significant difference in central tendency between the two groups, significance is set at $\alpha = 0.05$. All statistical tests will be two-sided. The results of these tests will be reported in 95% confidence Interval and p-value for the Student's t-test and in Mann-Whitney U and p-value for the Mann-Whitney U test.

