11.4.5 Interim analysis

An interim analysis will be conducted when the first 10 interventional patients have reached 4.5 months follow-up (Visit 4). All available data will be assessed, analyzed and evaluated equivalently to the full data analysis. To mitigate the risk for type II error, stopping criteria only include the primary outcome variable. Statistically significant ($P \leq 0.05$) inferiority of the interventional treatment in the primary outcome variable will lead to premature termination of the trial.

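### The 20-patient interim analyses every outcome by arm and may be published with no embargo, so uncontrolled early results can reach the trial while it is still running

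*Combined protocol and SAP*

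**What the plan says.** - **Scope of the interim.** Section 11.4.5 triggers the interim when the first 10 interventional patients reach Visit 4 (4.5 months) and states: "All available data will be assessed, analyzed and evaluated equivalently to the full data analysis". Section 11.4 sets the level at 0.05 and adds: "All statistical tests will be two-sided". The interim therefore tests for benefit as well as harm, on every outcome available by then.
- **Stopping rule.** Sections 11.3 and 11.4.5 name one criterion, significant inferiority (P at or below 0.05) on tunnel volume. Section 11.3 says that this finding "with a total of 20 patients (10 interventional, 10 control) will lead to premature termination of the study". There is no rule for stopping on benefit, and no alpha is allocated to the interim.
- **Publication.** Section 13 says the sponsor-investigator will try to "publish the data of the interim analysis, the primary endpoint analysis and the full data analysis in a peer-reviewed medical journal". The interim is a separate item in that list, and nothing says when it may appear.
- **Confirmatory test.** Sections 5.1, 11.1 and 11.4.2 place it at Visit 5 (12 months). The Visit 4 comparison is labelled supportive.
- **Who is blinded.** Section 6.3.2: "The current clinical trial is designed as a patient-blinded study". The same section says the operator cannot be blinded. Section 9.2.2.2: "KT-1000 Arthrometer-, Lachman- and Pivot-shift testing are performed by the PI". Under Section 6.4, patients learn their allocation only at their own study end.

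**The concern.** An interim meant as a harm check needs one comparison and the safety tables. This one runs the whole efficacy plan by arm, and Section 13 makes the result a publication. Two things follow.

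First, a nominally significant benefit at 4.5 months in 20 patients could enter the literature as a result of this trial, with no level set for it and before the 12-month comparison exists.

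Second, by-arm results could reach people who still influence the data. Final eligibility is judged in the operating theatre before allocation (Section 9.3.2.3.2). The principal investigator also performs the KT-1000, Lachman and pivot-shift tests, and the last two are graded manually. Knowing which arm is ahead could affect who is entered and how borderline grades are scored. For patients the route is narrower: a published result can change expectation in the patient-reported scores.

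**Working it through.** **1. The plan's own sample size.** Section 11.2: "It is aimed to detect a 20% difference in relative change of bone tunnel volume between the two groups". With SD 25.175, two-sided 0.05 and power 0.80:

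n per group = 2 x (1.960 + 0.842)^2 x (25.175/20)^2 = 24.9, so 25.

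Total = 50/0.9 = 55.6, so 56. Both stated figures reproduce.

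**2. When the interim falls** (rates from Section 6.2, visit window from the study schedule).

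- Accrual: 12 x 0.60 x 0.35 = 2.52 per month; recruitment ends at 56/2.52 = 22.2 months.
- Patient 20 enters at 20/2.52 = 7.9 months and reaches Visit 4 at 7.9 + 4.5 = 12.4 months (11.4 to 13.4 with the 1-month window).
- Enrolled by then: 12.4 x 2.52 = about 31 (29 to 34). Still to be randomised: about 25.
- Recruitment left: 22.2 - 12.4 = 9.8 months (8.8 to 10.8).
- Past 12 months: (12.4 - 12) x 2.52 = about 1 patient, or about 6 if everyone used the early edge of the 2-month Visit 5 window.

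The Synopsis allows about 6 months for statistics and abstract at the end of the study. If the same held for the interim (an assumption), an abstract would be ready at about month 18.4, before recruitment ends. A paper falls within recruitment only if it appears within about 9.8 months of the interim data. Otherwise it can still fall within follow-up, which runs to month 82.

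**3. What 10 per arm can show.** At the planned SD, significance needs an observed difference of at least 2.101 x 25.175 x sqrt(2/10) = 23.7 points. Power for a true 20-point difference is 0.39 (noncentral t). Any significant interim benefit at that SD would therefore exceed the 20-point target, so a published one would tend to overstate the effect.

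**4. Error rates on tunnel volume.** Let Z1 be the interim statistic (20 patients, 4.5 months) and Z2 the final one (50 patients, 12 months). Under no effect they are bivariate normal with correlation rho x sqrt(20/50), where rho is the within-patient correlation of the 4.5- and 12-month changes. The documents give no rho, so it is varied from 0 to 1.

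| rho | corr(Z1, Z2) | False benefit at either look: P(Z1 > 1.96 or Z2 > 1.96) | Significant in either direction at either look | False benefit at Visit 5 only, with the harm stop |
|---|---|---|---|---|
| 0 | 0 | 0.0494 | 0.0975 | 0.0244 |
| 0.5 | 0.316 | 0.0475 | 0.0949 | 0.0249 |
| 0.7 | 0.443 | 0.0461 | 0.0923 | 0.0250 |
| 1 | 0.632 | 0.0432 | 0.0863 | 0.0250 |

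The last column is the plan as written, and it does not exceed 0.025. The third column applies only if a significant interim result is also taken as a claim. A t-test simulation (200,000 runs per value of rho) agrees, giving 0.044 to 0.049 for the third column.

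**5. Other outcomes.** The table covers tunnel volume alone. For scale, 6 to 8 independent outcomes each tested at 0.05 give 1 - 0.95^6 = 26% to 1 - 0.95^8 = 34% for at least one false positive at the interim. Independence is an assumption and overstates the risk for correlated outcomes.

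**The case against.** The strongest reply is that nothing confirmatory is damaged. Only Visit 5 is confirmatory, Visit 4 is supportive, and the interim can end the trial only for inferiority. That stands. A reader might infer that the plan spends its 0.05 twice; the documents do not support this, and the last column of the table shows why.

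A reader might also infer that publication during recruitment is planned. Section 13 gives no date, so this is a possibility drawn from the accrual figures.

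The routes to bias have limits:

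- Group means do not tell patients their own arm. A change in expectation would act on both arms and does not by itself create a difference between them.
- The operator and the assessing investigator are exposed to allocation anyway; interim knowledge adds to that by an amount that cannot be quantified here.
- Allocation follows the eligibility decision and uses sealed envelopes (Sections 7.3 and 9.3.2.3.2). Changed selection would mainly alter who enters, not the balance between arms, unless concealment failed.
- The primary outcome is a voxel-based CT volume (Section 9.2.1), and none of these routes has been shown to bias it.

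It cannot be said that no firewall exists. The available text does not state who runs or receives the interim, but the material between the study schedule and Section 2 is not available to this review.

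The differing trigger wording, first 10 interventional patients against 10 + 10, is minor, because Sections 6.3.1 and 7.3 make the first block exactly 10 + 10. At most a few late controls could be short of Visit 4.

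None of this removes the two explicit statements: a full by-arm analysis at the interim, and its publication without an embargo.

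**Conclusion.** The point holds as a defect in interim scope and release, not as an error in the confirmatory test. As written, the plan generates by-arm efficacy results at about month 12.4, with about 25 of 56 patients still to be randomised and nearly all 12-month CTs outstanding, and it leaves their publication date open. The false-benefit rate of the Visit 5 test stays at or below 2.5% (two-sided 5%). The 4.3-4.9% figure is conditional on a significant 4.5-month result being read as a claim. It also assumes 50 patients at the final test and a correlation between 1 and 0. The timing assumes the planned accrual rate. The influence on selection and stability grading is plausible but unquantified; for patients it is limited to expectation.

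**What to change.** - **Section 11.4.5:** limit the interim to the Visit 4 CT inferiority check and the adverse-event tables. State that no superiority test is done or reported, and that only stop or continue is passed to the operating and assessing investigators.
- **Section 13:** release by-arm interim data only after the Visit 5 primary analysis is locked.
- **Sections 11.3 and 11.4.5:** use the same trigger in both, the first block of 10 + 10 having reached Visit 4.

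The cost is a later interim paper. The last Visit 5 falls at 22.2 + 12 = 34.2 months, or 36.2 with the 2-month window, against 12.4 for the interim: a delay of about 22-24 months. Sample size and final alpha are unchanged.

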14 FUNDING AND SUPPORT

This study will mainly be financed by ZuriMED Technologies AG.

15 INSURANCE

The trial is covered by insurance by "Winterthur Versicherung" (Insurance number: 14.050.565). The insurance certificate is deposited at the cantonal ethics committee. For insurance coverage, patients must follow the instructions by the PI. The patient must report the occurrence of any health related complication to the PI. In such a case, as far as necessary, representatives of the insurance company may be granted access to the health-related patient data.

17 APPENDICES

- Instructions for use SmartBone
- TechInfos SmartBone
- EC Certificate SmartBone
